10.5 Other Required Reporting

10.51 Unanticipated Problems Involving Risks to Subjects or Others (UPIRTSOS) in general, include any incident, experience, or outcome that meets all of the following criteria:

1. Unexpected (in terms of nature, severity, or frequency) given (a) the research procedures that are described in the protocol-related documents, such as the IRB-approved research protocol and informed consent document; and (b) the characteristics of the subject population being studied;

2. Related or possibly related to participation in the research (in this guidance document, possibly related means there is a reasonable possibility that the incident, experience, or outcome may have been caused by the procedures involved in the research); and
3. Suggests that the research places subjects or others at a greater risk of harm (including physical, psychological, economic, or social harm) than was previously known or recognized.

Some unanticipated problems involve social or economic harm instead of the physical or psychological harm associated with adverse events. In other cases, unanticipated problems place subjects or others at increased *risk* of harm, but no harm occurs.

Note: If there is no language in the protocol indicating that pregnancy is not considered an adverse experience for this trial, and if the consent form does not indicate that subjects should not get pregnant/impregnate others, then any pregnancy in a subject/patient or a male patient's partner (spontaneously reported) which occurs during the study or within 120 days of completing the study should be reported as a UPIRTSO.

If the event meets the criteria for an UPIRTSO, submit to your IRB as required by your institutional policies.

10.52 Baseline and Adverse Events Evaluations

“Investigators should complete all routine and standard of care assessments to evaluate for toxicity and symptoms of drug-induced adverse events. This may include, but is not limited to, verbal reports from the patient and/or caregiver, physical examination and laboratory findings. Adverse events should be reported throughout the course of the study, until the study termination visit, and followed through to resolution”.

10.521 Adverse events to be graded at each evaluation and pretreatment symptoms/conditions to be evaluated at baseline per the CTCAE v4.0 grading:

System Organ Class	Adverse Event Symptom(s)	Baseline	Each Evaluation
Blood and lymphatic system disorders	Febrile neutropenia		X
Gastrointestinal	# stools per day	X	
	Diarrhea		X
	Nausea	X	X
	Vomiting	X	X
General disorders and administration site conditions	Edema limb	X	X
	Periorbital edema	X	X
	Fatigue	X	X
Investigations	Aspartate aminotransferase (AST) increase	X	X
	Alanine aminotransferase (ALT) increase	X	X
	Alkaline phosphatase, serum (ALK) increase	X	X
	Blood Bilirubin increase	X	X
	Neutrophil count decrease	X	X
	Platelet count decrease	X	X
Metabolism and nutrition disorders	Hypokalemia	X	X
Renal and urinary disorders	Serum creatinine increase	X	X

10.53 Submit via appropriate Academic and Community Cancer Research United (ACCRU) Case Report Forms (i.e., paper or electronic, as applicable) the following AEs experienced by a patient and not specified in Section 10.5:

10.531 Phase I/Ib:

All AEs deemed *possibly, probably, or definitely* related to the study treatment or procedure, regardless of Grade

10.532 Phase II:

Grade 1-2 AEs deemed *possibly, probably, or definitely* related to the study treatment or procedure.

Grade 3 and 4 AEs regardless of attribution to the study treatment or procedure.

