2.2 Phase Ib Portion

2.21 Primary Aim: To assess, in a preliminary fashion, antitumor efficacy, in terms of Disease Control Rate and further tolerability of the recommended dose level of combination of nal-IRI and 5-FU with rucaparib in patients with metastatic disease from pancreatic cancer (≤ 1 line of prior therapy in the metastatic setting).

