10.31 Special Situations for Expedited Reporting

10.311 EXPECTED Serious Adverse Events: Protocol Specific Exceptions to Expedited Reporting

For Phases I and Ib of this study, all Serious Adverse Events will be subject to Expedited Reporting (as defined in Section 10.41). The list of Expected Serious Adverse Events and associated grades will be reviewed and determined by the study team after the completion of the Phase 1b portion of the study.

10.312 Death

- Any death occurring within 30 days of the last dose, regardless of attribution to an agent/intervention under an IND/IDE requires expedited reporting within 24-hours.
- Any death occurring greater than 30 days with an attribution of possible, probable, or definite to an agent/intervention under an IND/IDE requires expedited reporting within 24-hours.
- **Reportable categories of Death**
 - Death attributable to a CTCAE term.

- Death Neonatal: A disorder characterized by cessation of life during the first 28 days of life.
- Death NOS: A cessation of life that cannot be attributed to a CTCAE term associated with Grade 5.
- Sudden death NOS: A sudden (defined as instant or within one hour of the onset of symptoms) or an unobserved cessation of life that cannot be attributed to a CTCAE term associated with Grade 5.
- Death due to progressive disease should be reported as **Grade 5 “Neoplasms benign, malignant and unspecified (including cysts and polyps) – Other (Progressive Disease)”** under the system organ class (SOC) of the same name. Evidence that the death was a manifestation of underlying disease (e.g., radiological changes suggesting tumor growth or progression: clinical deterioration associated with a disease process) should be submitted.

10.313 Secondary Malignancy

- A **secondary malignancy** is a cancer caused by treatment for a previous malignancy (e.g., treatment with investigational agent/intervention, radiation or chemotherapy). A secondary malignancy is not considered a metastasis of the initial neoplasm.
- All secondary malignancies that occur following treatment with an agent under an IND/IDE to be reported. Three options are available to describe the event:
 - Leukemia secondary to oncology chemotherapy (e.g., acute myeloid leukemia [AML])
 - Myelodysplastic syndrome (MDS)
 - Treatment related secondary malignancy
- Any malignancy possibly related to cancer treatment (including AML/MDS) should also be reported via the routine reporting mechanisms outlined in each protocol.

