- 16.228 DL2-A (formerly known as DL1-A) was added as an intermediate dose level between DL 1 and DL2-B (formerly known as DL2) (Amendment 3). Following the approval of Amendment 3, enrollment will re-open to DL2-A. If DLTs are seen in less than 2 out of 6 patients treated at DL2-A then DL2-A will be considered the MTD. If DLTs are observed in at

least 2 patients treated at DL2-A then enrollment will resume at the next lowest DL until MTD is met.

- 16.23 Analysis plans: All the relevant results pertaining to toxicity, MTD, laboratory correlates will be examined in an exploratory and hypothesis-generating fashion.
- 16.231 Adverse events profile: The number and severity of all adverse events (overall, by dose-level, and by tumor group) will be tabulated and summarized in this patient population. The grade 3+ adverse events will also be described and summarized in a similar fashion. This will provide an indication of the level of tolerance for this treatment combination in this patient group
- 16.232 Toxicity Profile: The term toxicity is defined as adverse events that are classified as either possibly, probably, or definitely related to study treatment. Non-hematologic toxicities will be evaluated via the ordinal CTC standard toxicity grading. Hematologic toxicity measures of thrombocytopenia, neutropenia, and leukopenia will be assessed using continuous variables as the outcome measures (primarily nadir) as well as categorization via CTC standard toxicity grading. Overall toxicity incidence as well as toxicity profiles by dose level, patient and tumor site will be explored and summarized.
- 16.233 Response: Objective responses, as defined per RECIST 1.1, will be summarized by simple descriptive summary statistics delineating complete and partial responses as well as stable and progressive disease.

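### Phase I/Ib leaves out non-serious, unsolicited clinical AEs judged unlikely or unrelated, even at grade 3-4, so the Phase I tables in 16.231 would be incomplete and these events cannot be reviewed centrally in Phase Ib

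*Combined protocol and SAP*

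**What the plan says.** Section 10.53 sets out which AEs go onto case report forms beyond those already specified. For Phase I/Ib, 10.531 asks for every event judged at least possibly "related to the study treatment or procedure, regardless of Grade". For Phase II, 10.532 asks for related events at grade 1-2 and, separately, "Grade 3 and 4 AEs regardless of attribution to the study treatment or procedure".

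The Phase I analysis plan has two distinct safety items. Section 16.231 states: "The number and severity of all adverse events (overall, by dose-level, and by tumor group) will be tabulated and summarized in this patient population". It adds: "The grade 3+ adverse events will also be described and summarized in a similar fashion". Section 16.232 is narrower: "The term toxicity is defined as adverse events that are classified as either possibly, probably, or definitely related to study treatment".

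The Phase Ib primary aim (2.21) includes "further tolerability of the recommended dose level of combination of nal-IRI and 5-FU with rucaparib". Its analysis plan (16.31) says only that relevant toxicity results will be examined in an exploratory way.

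The Phase II text provides for looking again at events called unrelated or unlikely: grades 3-5 in 16.432c, and grades 4-5 in the bullet that follows 16.522. The Phase I/Ib text has no counterpart.

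**The concern.** Because 16.232 already covers the related events, 16.231 must mean something wider. The collection rule in 10.531 does not supply all of that wider set.

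The phases are also ordered oddly. Attribution carries most weight in the early phases: an event can be a dose-limiting toxicity (DLT) under 7.42 only if judged at least possibly related, and tolerability is part of the Phase Ib aim. Yet the phase that collects severe events regardless of attribution is Phase II. In a single-arm study of a new combination in advanced cancer, a symptom such as dyspnea or a minor infection is easily put down to the disease. If several investigators did so, the study team would have no submitted record of those events and no planned review that could notice the pattern. Section 16.52 lets the team suspend accrual for an unexpected AE profile, but the team can act only on what it receives.

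**Working it through.** No figure in the plan depends on this point, so the check is mainly a reconciliation of text.

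**1. How 10.53 is read.** It excludes AEs specified in Section 10.5, the section to which it belongs. I take the intended exclusion to be the solicited list in 10.521.

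**2. Routes that bypass the attribution filter in Phase I/Ib.**

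| Route | Where | Effect |
|---|---|---|
| Solicited terms | 10.521: "Adverse events to be graded at each evaluation and pretreatment symptoms/conditions to be evaluated at baseline per the CTCAE v4.0 grading" | 15 terms marked for each evaluation, no attribution condition |
| SAEs | 10.311: "For Phases I and Ib of this study, all Serious Adverse Events will be subject to Expedited Reporting (as defined in Section 10.41"); 10.4 | Reported whether or not related; 10.1(g) also sends them to routine data |
| AESIs | End of 10.4 | Secondary leukemia, myelodysplastic syndrome and pneumonitis, serious or not; 10.1(g) applies |
| Deaths | 10.541 | Within 30 days of last treatment, any attribution |
| Laboratory results | Section 4.0; forms in 18.1 | Day 1 and Day 15 of each cycle, no attribution condition |

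**3. What is left.** An event is missed only if it is non-serious, not an AESI, not one of the 15 terms, clinical rather than laboratory, and judged unlikely or unrelated. Dyspnea and infection are not among the 15 terms, so their non-serious forms can fall in this set. Grade 3 events can too, as can any grade 4 event not classed as serious.

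**4. Against the analysis plan.** The Phase I tables in 16.231 call for this residual set and 10.531 does not collect it. Phase Ib (16.31) promises no table of all AEs, so the issue there is that attribution cannot be reviewed.

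**5. Patients affected.** Section 16.12 gives 49-58 patients for Phase I including 40 in Phase Ib. Dose escalation is therefore 49 − 40 = 9 to 58 − 40 = 18 patients.

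**6. Illustration only.** The documents give no rate. Suppose 15-35% of patients had at least one such event at grade 3-4. Then 0.15 × 9 ≈ 1 to 0.35 × 18 ≈ 6 dose-escalation patients, and 0.15 × 40 = 6 to 0.35 × 40 = 14 Phase Ib patients, would have events that are not submitted.

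Section 16.21 says that a toxicity with 25% incidence is seen in 6 patients with probability at least 82%. This reproduces: 1 − (1 − 0.25)^6 = 0.822. If a share m of a non-serious, unsolicited event type were wrongly called unrelated, independently between patients, the chance that at least one is submitted is 1 − (1 − 0.25(1 − m))^6:

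- m = 10%: 0.783
- m = 20%: 0.738
- m = 30%: 0.685
- m = 50%: 0.551

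The documents do not say that any such misattribution occurs.

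**The case against.** The strongest reply is that the filter lets through little that matters. Anything serious is captured, the most expected toxicities are solicited, and the threshold for a possible relation in 10.3 is low: the event need only be one that may be related. Collecting only related events outside the solicited list is also a recognised way to limit site burden. Much of this stands. It keeps the gap small, but it does not make 16.231 achievable as worded, and it does not explain why Phase II applies the stricter rule.

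The general sentence in 10.52 that AEs should be reported throughout the study could be cited against the gap. It does not override the specific form-submission rule in 10.531. The expedited-reporting table in 10.4 includes grade 3 events without hospitalization, but its lead-in confines it to serious events.

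A reader might infer more than the documents support:

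- *That attribution cannot be checked at all in Phase I/Ib.* It can be, for every route listed under the working.
- *That pneumonitis or anemia would go unseen.* Pneumonitis is an AESI even when non-serious. Blood counts are scheduled twice per cycle and have their own forms, so low hemoglobin should be recoverable, although the form fields are not listed.
- *That the recommended dose is biased.* Under 7.413-7.414 it rests on DLTs and on discussion between the study team and the sponsor, not on the exploratory 16.231 tables. A dose reduction in the DLT window, or a hold of more than 28 days for any reason, also counts as a DLT (7.42).
- *That the stopping rules differ between phases in this respect.* Both 16.521 and 16.522 count only related events. The difference lies in the added review of events called unrelated or unlikely.

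**Conclusion.** The mismatch is real and narrow. Followed as written, 10.531 leaves the 16.231 tables of all AEs and of grade 3+ AEs incomplete for the 9-18 dose-escalation patients. It also leaves the 40 Phase Ib patients without the central check on attribution that Phase II has. Only non-serious, non-AESI, unsolicited clinical events judged unlikely or unrelated are affected.

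How many events that is cannot be learned from the documents; the illustrative counts rest wholly on an assumed rate. The conclusion itself needs only two readings: that 10.53 means to exclude the 10.521 list, and that laboratory results reach the database through their own forms. No primary endpoint fails, and there is no demonstrated effect on the recommended dose. This is a cheap improvement worth making, chiefly for Phase Ib.

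**What to change.** 1. In 10.531, keep the present rule for related events of any grade and add *plus every grade 3 or 4 AE, whatever its attribution*, matching 10.532. Section 7.12 records that dose escalation has already selected DL2-A, so this takes effect mainly in Phase Ib.
2. Extend to Phase I/Ib the Phase II review of grade 3-5 events judged unrelated or unlikely (16.432c and the bullet after 16.522).
3. Reword 16.231 so that its tables cover the events actually collected under 10.521, 10.531, 10.54 and expedited reporting. This resolves the Phase I mismatch, which new collection can no longer do for patients already treated.
4. While editing, correct the cross-reference in 10.53, which appears to mean the solicited list in 10.521.

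The cost is a few sentences in an amendment and somewhat more data entry on the existing *Adverse Events: Other* form. No new form, visit or analysis method is needed.

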10.54 Grade 5 AEs (Deaths)

10.541 Any death \leq 30 days of the patient's last study treatment or procedure regardless of attribution to the study treatment or procedure.

10.542 Any death $>$ 30 days after the patient's last study treatment or procedure that is felt to be at least possibly treatment related must also be submitted as a Grade 5 AE, with a CTCAE type and attribution assigned.

10.55 Refer to the instructions in the CRF Packet (or electronic data entry screens, as applicable) regarding the submission of late occurring AEs following completion of the Active Monitoring Phase (i.e., compliance with Test Schedule in Section 4.0).

10.56 Reconciliation: Clovis will send Research Coordinating Center a monthly listing of SAEs received by Clovis from Research Coordinating Center in connection with the Trial and any SUSARs sent to Research Coordinating Center from Clovis. Research Coordinating Center will review the listing and notify Clovis of any omissions.

10.57 Quarterly Report: Research Coordinating Center will provide Ipsen with accrual and a toxicity report on a quarterly basis.

11.0 Treatment Evaluation Using RECIST Guideline

Response and progression will be evaluated in this study using the new international criteria proposed by the revised Response Evaluation Criteria in Solid Tumors (RECIST) guidelines (version 1.1 (Eisenhauer EA, Therasse P, Bogaert J, *et al.*, 2009)). Changes in the largest diameter (unidimensional measurement) of the tumor lesions and the short axis measurements in the case of lymph nodes are used in the RECIST guideline.

11.1 Schedule of Evaluations: For the purposes of this study, patients should be reevaluated every 8 weeks.

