4.0 Test Schedule

NOTE: Variation of ≤ 4 days of scheduled visit is permitted.

Tests and procedures	≤ 21 days prior to registration	≤ 7 days prior to registration	Active Monitoring				
			Prior to dosing on Day 1 of each cycle,* Beginning with Cycle 1 (until PD)	Day 15 of each cycle, Beginning with Cycle 1 (until PD)	Prior to 3 rd and subsequent odd cycles (until PD)	End of Treatment (PD, withdrawal, or removal)	Observation ⁸ : 30 days of End of Treatment
History and exam, wt, ECOG PS	X		X	X		X	X
Height	X						
Adverse event assessment	X		X	X		X	X ⁷
Hematology: CBC/ differential	X		X	X		X	X
Chemistry: SGOT (AST), SGBT (ALT), alk phos, T. bili, creatinine, calcium, phos, glucose, Na, K							
Tumor measurement ¹	X				X	X	
Pregnancy test ²		X	X				
Mandatory archival tissue collection ^{5, R} (See Section 17)	X						
cfDNA ^{4, R}			X		X	X	
ECG ⁶	X		X				
Cancer markers: CEA (colorectal cancer) and CA19-9 (cholangiocarcinoma) ^{4 R}	X				X	X	
Patient Medication Diary ³			X			X	

* Cycle = 28 days.

(Footnotes on next page)

1. Imaging should be done using CT scan (MRI if CT is not feasible). Use same imaging throughout the study. If patient is on study for more than 2 years, allow scans 3-4 months apart.
2. For individuals of childbearing potential only. Negative urine or serum pregnancy test must be done \leq 7 days prior to registration and repeated prior to dosing on day 1 of each cycle. If a patient becomes pregnant during the study the investigator is to stop dosing with study drug(s) immediately. (See Section 10.314 for additional information.)
3. The diary must begin the day the patient starts taking the medication and must be completed per protocol and returned to the treating institution OR compliance must be documented in the medical record by any member of the care team.
4. Mandatory blood draws (STRECK, EDTA and No Additive tubes) for research should not be collected and submitted until after the patient is registered onto the study, and should be done prior to dosing on Cycle 1, Day 1, then Day 1 of subsequent odd cycles, and end of treatment. Kits are required for this collection (See Section 14.0).
5. Receipt of archival tumor tissue is not required for study registration and initiation of therapy. However, it is mandatory to receive the required tissue within 60 days from registration.

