8.2 Dose Modifications for Hematologic Toxicities

Worst Toxicity by CTCAE Grade ^{b, c}	nal-IRI or 5-FU ^e
Grade 2 neutropenia (ANC < 1500 – 1000 cells/mm ³)	100% of previous dose
Grade 3 or 4 neutropenia (ANC ≤ 1000 cells/mm ³) or febrile neutropenia ^a	^{1st} occurrence: Delay treatment ^d until resolved to ≤ Grade 2, then reduce dose to by 25% ^{2nd} occurrence: Delay treatment ^d until resolved to ≤ Grade 2, then reduce dose another 25% (50% of original dose)
≤Grade 2 thrombocytopenia (Grade 2: platelets ≤75,000/mm ³ -50,000/mm ³)	If Grade 2: 100% of previous dose
Grade 3-4 thrombocytopenia: platelets <50,000/mm ³)	If Grade ≥3: ^{1st} occurrence: Delay treatment ^d until resolved to ≤ Grade 2, then reduce dose by 25% ^{2nd} occurrence: Delay treatment ^d until resolved to ≤ Grade 2, then reduce dose another 25% (50% of original dose)

^aConsider the use of G-CSF for patients who experience ≥ Grade 3 neutropenia or febrile neutropenia.

^bAnemia: no changes; transfuse as needed.

^cLymphocytopenia: no changes.

^dFor Grade 3 and worse neutropenia and/or platelets, delay all agents (5FU, leucovorin, nal-IRI and rucaparib) until resolve to ≤ Grade 2.

^eThe dose of the agent (5FU or nal-IRI) that is most likely the cause of the hematologic toxicity, as per investigator's assessment, will be reduced when resuming treatment.

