Grade ≥ 4	
 • Hold rucaparib • Monitor liver function tests weekly until resolution to \leq Grade 2 		Resume with a dose reduction and monitor liver function tests weekly for 3 weeks after restarting.

a. NCI-CTCAE = National Cancer Institute - Common Terminology Criteria for Adverse Events, version 4.03

b. Treatment with rucaparib should be held until the toxicity resolves to \leq CTCAE Grade 2. Twice daily dosing may then be resumed at either the same dose or a lower dose, per investigator discretion. If treatment is resumed at the same dose, and the patient experiences the same toxicity, the dose should be reduced following resolution of the event to \leq CTCAE Grade 2. If the patient continues to experience toxicity, additional dose reduction steps are permitted; however, the investigator should contact ACCRU (see Protocol Resource page) before reducing to 300 mg BID. If a patient continues to experience toxicity despite dose reduction steps to 300 mg BID, or if dosing with rucaparib is interrupted for $>$ 14 consecutive days due to toxicity, treatment should be discontinued, unless otherwise agreed between the investigator and ACCRU.

8.3 Dose Modifications for Non-Hematologic Toxicities Other than grade 3 ALT/AST (follow recommendation by Table 8.22), Fatigue and Grade 3 Anorexia^{a, d}

Worst Toxicity by CTCAE Grade*	na1-IRI	5-FU
Grade 1 diarrhea ^b	Continue same dose	Continue same dose
Grade 1 or 2 including diarrhea (except alopecia, nausea and vomiting)	Withhold na1-IRI then resume once resolved to grade 1 at 100% of previous dose	Withhold 5-FU, then resume once resolved to grade 1 at 100% of previous dose, except for Grade 2 hand foot syndrome, Grade 2 cardiac toxicity, or any grade neurocerebellar toxicity
Grade 3 or 4, including diarrhea ^c (except alopecia, nausea and vomiting)	Withhold na1-IRI then resume once resolved to grade 1 per below: 1 st occurrence: Reduce dose to by 25% 2 nd occurrence: Reduce dose another 25% (50% of original dose)	Withhold 5-FU then resume once resolved to grade 1 per below: 1 st occurrence: Reduce dose by 25% 2 nd occurrence: Reduce dose another 25% (50% of original dose) *except for Grade 3 or 4 hand foot syndrome

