16.43 Phase II Analysis Plan

16.431 Primary Endpoint Analysis - Estimation: The proportion of best response ≤ 32 weeks will be estimated by the number of evaluable patients who reach CR/PR, per RECIST 1.1, ≤ 32 weeks since registration divided by the total number of evaluable patients. Confidence intervals for the proportion will be calculated according to the approach of Duffy and Santner (1987).

16.432 Secondary Endpoint Analyses

16.432a Overall survival: Survival time is defined as the time from registration to death due to any cause. Patients who fail to return for evaluation after beginning therapy will be censored for survival on the last day of therapy or date last known to be alive, whichever is later. The distribution of survival time will be estimated using the method of Kaplan-Meier (1958).

16.432b Progression-free survival: Progression-free survival is defined as the time from registration to the earliest date documentation of disease progression or death due to any cause. Patients who fail to return for evaluation after beginning therapy will be censored for progression on the last day of therapy or date last known to be alive, whichever is later. The distribution of progression-free

survival will be estimated using the method of Kaplan-Meier (1958).

16.432c Toxicity: As per NCI CTCAE version 4.03, the term toxicity is defined as adverse events that are classified as either “possibly,” “probably,” or “definitely related” to study treatment. The maximum grade for each type of toxicity will be recorded for each patient, and frequency tables will be reviewed to determine toxicity patterns within patient groups. In addition, we will review all adverse event data that is graded as 3, 4, or 5 and classified as either “unrelated” or “unlikely to be related” to study treatment in the event of an actual relationship developing. Adverse events and toxicities will be evaluated using all patients who have received any study treatment as well as summarizing those who have been included in the efficacy analyses. The overall adverse event rates for grade 3 or higher adverse events will be compared using Chi-Square or Fisher’s Exact tests between the two treatment groups.

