1. Prior to 3rd and subsequent odd cycles (until PD). Upload a copy of documentation of progression in RAVE on the Supporting Documentation Form.
2. Submit only if applicable.
3. Day 1 of each cycle, beginning with Cycle 1 (until PD).
4. Day 15 of each cycle, beginning with Cycle 1 (until PD).

Follow-up Material(s)

CRF	Event Monitoring Phase ¹				
	q. 6 months until PD ²	At PD ²	After PD q. 6 mos.	Death	At Each Event Occurrence
Patient Status: Survival and Disease Status Follow-Up/Event Monitoring	X ²	X ²	X	X	
Adverse Events: Late ³					X
Notice of New Primary ³					X
Consent Withdrawal (choose appropriate form) ³					X
• Consent Withdrawal: Specimen Only					
• Consent Withdrawal: Clinical Follow-Up Only					
• Consent Withdrawal: All Follow-Up					
Lost to Follow-Up ³					X
ACCRU Deviation Form ³	X ³	X ³	X ³	X ³	

1. If a patient is still alive 3 years after registration, no further follow-up is required.
2. Upload a copy of documentation of progression in RAVE on the Supporting Documentation Form.
3. Submit only if applicable.

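### Tumour scans are set by the calendar in 11.1 but by cycle number in 4.0 and 18.1, and nothing says which governs once a cycle is delayed

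*Combined protocol and SAP*

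**What the plan says.** Section 11.1 sets the interval by the calendar: "For the purposes of this study, patients should be reevaluated every 8 weeks". It names no starting point and does not mention treatment delay.

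The 4.0 test schedule ticks tumour measurement in the column for the third "and subsequent odd cycles (until PD"). Footnote 1 to the RECIST form in 18.1 uses the same rule: "Prior to 3rd and subsequent odd cycles (until PD"). A cycle is 28 days. The general note in 4.0 reads "Variation of ≤ 4 days of scheduled visit is permitted". Footnote 1 of 4.0 allows scans 3-4 months apart after 2 years on study.

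Section 8 provides for delay:
- For grade 3 or worse neutropenia or low platelets, 8.2 footnote d says to "delay all agents (5FU, leucovorin, nal-IRI and rucaparib) until resolve to ≤ Grade 2".
- Section 8.3 withholds nal-IRI and 5-FU for a range of non-hematologic events, for some of them "then resume once resolved to grade 1 at 100% of previous dose".
- Footnote b of 8.22 limits a rucaparib interruption: after more than "14 consecutive days due to toxicity, treatment should be discontinued, unless otherwise agreed between the investigator and ACCRU".

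The endpoints that depend on scan timing count from registration. The phase II primary endpoint is CR/PR within 32 weeks (16.41), and the stage 1 stopping clause looks at CR/PR/SD within 16 weeks (16.421). For the secondary endpoint, "Progression-free survival is defined as the time from registration to the earliest date documentation of disease progression or death due to any cause" (16.432b). Section 6.44 allows up to 21 days between registration and first dose.

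**The concern.** The calendar rule and the cycle rule give the same scan dates only while every cycle runs on time. After a delay of a week or more, which the 4-day allowance does not cover, 11.1 keeps the scan where it was. Sections 4.0 and 18.1 can be read as moving it to the next odd cycle. Two sites could each comply with the protocol and yet scan the same patient on different dates.

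Two things are at stake. The first is the primary endpoint: it counts responses seen inside a fixed number of weeks, so a scan pushed past week 32 cannot contribute. The second is PFS: progression is dated when documented, so the recorded date would depend on which section the site followed and, under the cycle rule, on toxicity.

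**Working it through.** **1. Agreement without delay.** Two cycles × 28 days ÷ 7 = 8.0 weeks. From first dose, both rules give weeks 8, 16, 24 and 32. The difference is 0.

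**2. Scan dates under the cycle rule with delay.** Let *s* be the weeks from registration to first dose (0 to 3, from 6.44) and *d* the weeks of delay per two cycles. *d* is an assumption, as is the premise that a delay moves Day 1. Scan *k* falls at week *s* + *k*(8 + *d*) from registration.

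| *s* | *d* | First four scans (week) | By week 32 | By week 16 |
|---|---|---|---|---|
| 0 | 0 | 8, 16, 24, 32 | 4 | 2 |
| 0 | 1 | 9, 18, 27, 36 | 3 | 1 |
| 0 | 2 | 10, 20, 30, 40 | 3 | 1 |
| 0 | 4 | 12, 24, 36, 48 | 2 | 1 |
| 3 | 0 | 11, 19, 27, 35 | 3 | 1 |
| 3 | 2 | 13, 23, 33, 43 | 2 | 1 |

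Two points follow. Even the on-time schedule puts a scan exactly on each limit (weeks 16 and 32), so any slip loses it. And a 21-day wait before the first dose has the same effect with no toxicity delay at all, if scans count from first dose. With *s* = 0 and *d* = 1, the last scan inside the window is at week 27, so a response first appearing between weeks 27 and 32 is not counted.

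**3. How often this could happen.** Four administrations fall in each pair of cycles. If each is delayed independently with probability 20% and every delay moves later cycles, the chance of reaching the second scan with no delay is 0.8^8 = 0.17. For the fourth scan it is 0.8^16 = 0.03. The 20% is illustrative.

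**4. Effect on PFS.** Simulation assumptions: exponential true progression with medians of 18 to 38 weeks; observed PFS is the first scan at or after progression; no deaths or symptomatic progression. Calendar scans fall every 8 weeks. Cycle-tied scans are separated by 8 + Binomial(4, *q*) × *d* weeks, where *d* is now the length of a single delay, *q* = 10-30% and *d* = 1 or 2.

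Mean observed PFS, cycle-tied minus calendar:
- one-week delays: about +0.2, +0.5 and +0.7 weeks at *q* = 10%, 20% and 30%
- two-week delays: about +1.0 and +1.5 weeks at *q* = 20% and 30%

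Kaplan-Meier landmarks over the same scenarios:
- week 26: −0.2 to about +6 points
- weeks 23, 31 and 39: lower in every scenario, by about 1 to 5 points

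For scale, the standard error of a 50% estimate with 24 patients is √(0.25/24) ≈ 10 points.

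The median also moves both ways. At *q* = 20% and *d* = 1 it falls from 32 to 29 weeks when the true median is 26, and rises from 32 to 35 when the true median is 30. The reason is that observed PFS can change only at scan times. Moving those times raises the curve just after a calendar scan. It lowers the curve just before the next one.

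**The case against.** The strongest reply is that the texts do not conflict as written: 11.1 states the interval, and 4.0 assigns it to visits. Footnote 1 of 18.1 belongs to a form-submission timetable and is weak evidence of a separate scan rule. No passage says that a delayed dose moves Day 1 of the next cycle, and the 18.1 treatment form covers omitted doses as well as delayed ones. A site that follows 11.1 has no slip. All of this stands. It makes the point an unresolved ambiguity and not a demonstrated bias, but it does not supply the missing rule.

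A reader might infer that PFS is lengthened, and most so in the patients with most toxicity. The documents do not support that. The mean rises, but 16.432b plans a Kaplan-Meier estimate, whose median and landmarks move in both directions. The simulation gives every patient the same delay probability, so it cannot show an effect concentrated in the most toxic patients. It also leaves out features that limit the slip: deaths are dated exactly, symptomatic deterioration counts as progression (11.45), 4.0 has a tumour measurement at end of treatment, and some patients with severe toxicity will stop treatment. PFS is a single-arm secondary estimate without a test, so no comparison between arms is affected.

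The loss at the stage 1 look should not be overstated either. The stopping clause counts stable disease, and one scan still falls inside 16 weeks in every row of the table.

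**Conclusion.** The point holds as an ambiguity that is cheap to remove. Sections 11.1, 4.0 and 18.1 give two anchors that separate after any delay longer than the 4-day allowance, and none of them says which governs.

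The firmer consequence is for the week-based windows. With one week of delay per two cycles and dosing from the day of registration, scans inside 32 weeks drop from 4 to 3 and inside 16 weeks from 2 to 1. This rests on the cycle rule being followed and on delays moving Day 1. Fewer scans in the window can only reduce the opportunity to record a response.

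For PFS, the supportable statement is that progression dates depend on which section a site follows. The mean shift is about 0.2 to 1.5 weeks under assumed delay rates of 10-30% per administration and delays of 1-2 weeks. No fixed direction of bias in the reported PFS curve, and no concentration in the most toxic patients, should be claimed.

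**What to change.** State one rule in 4.0, 11.1 and 18.1 footnote 1:

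- **Phase II:** tumour measurement every 8 weeks (± 4 days) from registration, regardless of treatment delays, until progression. Keep the 4.0 footnote 1 allowance for wider spacing after 2 years.
- **Limits:** count the week-16 and week-32 scans as inside the 16- and 32-week limits if they are taken within the ± 4-day window. Otherwise a scan done a day late, though permitted, would be lost.
- **Phase Ib:** anchor to first dose, because 16.11 times disease control from the start of study therapy.
- **cfDNA:** leave the draws on odd cycles.

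The registration anchor gives 4 scans by week 32 and 2 by week 16 for every phase II patient still being assessed, whatever the dosing history.

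The cost is wording plus some logistics. Some scans will not coincide with a Day 1 visit, and patients with long delays may have slightly more scans. A late start also brings the first scan closer to first dose: with the full 21 days allowed by 6.44, 8 − 3 = 5 weeks after it.
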